ABV	Alcohol by volume
ACE	Angiotensin-converting enzyme
ADE	Antibody-dependent enhancement
ADL	Activities of daily living
ADR	Adverse drug reaction
AE	Adverse event
AESI	Adverse event of special interest
BMI	Body mass index
CI	Confidence interval
CMH	Cochran-Mantel-Haenszel
COVID-19	Coronavirus disease 2019
CRO	Contract Research Organization
CSR	Clinical study report
CT	Computed tomography
CTCAE	Common Terminology Criteria for Adverse Events
DPI	Days post-infection
DSMB	Data and safety monitoring board
ECG	Electrocardiogram
eCRF	Electronic case report form
EOT	End-of-Treatment
GCP	Good Clinical Practice
HBcAb	Hepatitis B core antibody
HBsAb	Hepatitis B surface antibody
HBsAg	Hepatitis B surface antigen
HIV	Human immunodeficiency virus
IB	Investigator's brochure
ICF	Informed consent form
ICH	International Council for Harmonisation
IEC	Independent ethics committee
IgG1	Human immunoglobulin G1
IRB	Institutional review board
ITT	Intent-to-treat
ITTI	Intent-to-treat infected
IV	Intravenous
IVRS	Interactive voice response system
IWRS	Interactive web response system
MedDRA	Medical Dictionary for Regulatory Activities
NEWS2	National Early Warning Score 2
NOAEL	No-observed-adverse-effect level
PD	Pharmacodynamics
PK	Pharmacokinetics
RBD	Receptor binding domain
RT-PCR	Reverse transcription polymerase chain reaction
RT-qPCR	Reverse transcription quantitative polymerase chain reaction

SAE	Serious adverse event
SAS	Statistical Analysis System
SAP	Statistical Analysis Plan
SARS-CoV-2	Severe Acute Respiratory Syndrome Coronavirus 2
SoC	Standard of care
SOP	Standard operating procedure
SpO ₂	Saturation peripheral oxygen
SUSAR	Suspected unexpected serious adverse reaction
TEAE	Treatment-emergent adverse event
WHO	World Health Organization

1 Introduction

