1.2 CT-P59

CT-P59 is a human monoclonal antibody targeted against SARS-CoV-2 spike protein as a treatment for SARS-CoV-2 infection, which is manufactured by recombinant deoxyribonucleic acid technology in a Chinese hamster ovary mammalian cell line. The dosage form of CT-P59 is solution concentrate for dilution for administration in a single intravenous (IV) infusion.

The main mechanism of action is blocking the binding between SARS-CoV-2 RBD and cellular receptor, ACE2, thus inhibiting their infection to host cells. Although it has been known in many virus infections that antibodies can remove the virus-infected cells via antibody Fc-dependent function such as antibody-dependent cellular cytotoxicity, it is unlikely that CT-P59 induces antibody Fc-dependent virus clearance, considering the life cycle of SARS-CoV-2, which is assembled inside cells and released via exocytosis. However, it is postulated that there are additional mechanisms of CT-P59 mediated virus clearance by opsonization and complement activation (i.e., antibody-dependent, complement-dependent virolysis or antibody-dependent phagocytosis).

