5.2.1 Identity of CT-P59

CT-P59 is a monoclonal antibody which is being developed by the sponsor as a potential treatment for SARS-CoV-2 infection.

CT-P59 is supplied as a sterile, preservative-free solution of SARS-CoV-2 RBD binding monoclonal antibody in a 20 mL single use vial for IV infusion. CT-P59 is a clear to opalescent, colorless to pale yellow solution for injection, with a pH of 6.0 and 960 mg of SARS-CoV-2 RBD binding monoclonal antibody in 16 mL for IV infusion. One vial (16 mL) delivers 960 mg SARS-CoV-2 RBD binding monoclonal antibody, 13.12 mg of L-histidine, 15.84 mg of L-histidine monohydrochloride monohydrate, 8.0 mg of polysorbate 80, 505.584 mg of L-Arginine monohydrochloride, and water for injection. The container closure system includes type I borosilicate glass vial, Fluroetec Film coated rubber stopper and flip-off type aluminum cap.

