5.4 Blinding

This study will be double-blind, and will remain blinded to the investigator, all designated study staff (with the exception of the unblinded study pharmacists or unblinded staffs designated to prepare the study drug for infusion and predefined unblinded teams in the sponsor and CRO), and patients until the final CSR is generated.

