6.4 Virology and Serology Assessments

Viral shedding based on RT-qPCR or cell culture, genotyping and phenotyping of SARS-CoV-2 isolates will be performed using the nasopharyngeal swab samples for all patients.

Samples will be secured at the central laboratory for analysis and backup samples will be retained. Viral serology for SARS-CoV-2 antibody test with assays detecting serum antibodies against SARS-CoV-2 will also be performed locally using the serum samples (if the assay is available). The sample for virology and serology assessments will be collected for analysis at the time points specified in [Table 11-1](#) and [Table 11-2](#).

Details of biologic sampling time points and acceptable tolerance windows for virology assessments are described in [Table 6-2](#) and [Table 6-3](#).

Table 6-2 Nasopharyngeal Swab Sampling Time Points for Virology Assessment – Part 1

Day	Time point	Window
Day 1	Pre-dose	Pre-dose within the day
Day 2	24 hours after start of infusion	± 4 hours
Day 3	48 hours after start of infusion	
Day 4	72 hours after start of infusion	
Day 5	96 hours after start of infusion	
Day 6	120 hours after start of infusion	
Day 7	144 hours after start of infusion	
Day 10	216 hours after start of infusion	
Day 14	312 hours after start of infusion	± 1 day
Day 17	384 hours after start of infusion	
Day 21	480 hours after start of infusion	
Day 28*	648 hours after start of infusion	± 3 days

Abbreviation: RT-qPCR = reverse transcription quantitative polymerase chain reaction; SARS-CoV-2 = severe acute respiratory syndrome coronavirus 2

*If the RT-qPCR result on Day 28 shows positive of SARS-CoV-2 infection, additional viral shedding will be conducted on Day 90.

Table 6-3 Nasopharyngeal Swab Sampling Time Points for Virology Assessment – Part 2

Day	Time point	Window
Day 1	Pre-dose	Pre-dose within the day
Day 3	48 hours after start of infusion	± 4 hours
Day 7	144 hours after start of infusion	
Day 10	216 hours after start of infusion	
Day 14	312 hours after start of infusion	± 1 day
Day 21	480 hours after start of infusion	
Day 28*	648 hours after start of infusion	
		± 3 days

Abbreviation: RT-qPCR = reverse transcription quantitative polymerase chain reaction; SARS-CoV-2 = severe acute respiratory syndrome coronavirus 2

*If the RT-qPCR result on Day 28 shows positive of SARS-CoV-2 infection, additional viral shedding will be conducted on Day 90.

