26. Use of all prior and concomitant medications for the treatment of SARS-CoV-2 infection from the diagnosis of disease until the EOT visit, will be recorded in both the source documents and the eCRF. Use of all concomitant medications for other purposes, from within 30 days prior to the first administration of the study drug (Day 1) or from when the ICF is signed, whichever is earlier, will be recorded until the EOT visit.
27. Adverse events will be assessed from the date the patient signs the ICF until the last assessment date or EOT visit. Where an ADR (e.g., related to study drug) is ongoing at the EOT visit, the ADR will be followed up until one of the following: resolution or improvement from baseline, relationship reassessed as unrelated, confirmation from the investigator that no further improvement can be expected, end of collection of clinical or safety data, or final database closure. AEs of special interest (infusion related reactions [hypersensitivity/anaphylactic reactions]) should be closely monitored.

Table 11-2 Schedule of Assessments for Part 2

Study Day (Visit windows) ⁴	Screening ¹	Treatment Period											EOT ²	Follow-Up Period ³
	-7 to 1	1	2	3	5	7	10	14 (±1)	17 (±1)	21 (±1)	28 (±3)	56 (±5)	90 (±5)	Biweekly up to 180 (±5)
Telephone Follow-Up Visit														X
Informed consent	X													
Medical history	X													
Demographics	X													
Weight, BMI and height ⁵	X	X ⁶											X	
Hepatitis B/C and HIV test (central) ⁷	X													
Serum pregnancy test ⁸	X												X	
Inclusion/exclusion criteria	X	X ⁶												
Randomization		X ⁶												
Administration of study drug ⁹		X												
Nasopharyngeal swab ¹⁰														
• SARS-CoV-2 infection by sponsor-supplied rapid SARS-CoV-2 diagnostic test or RT-PCR ¹¹	X													
• Viral shedding (central, RT-qPCR), genotyping and phenotyping of SARS-CoV-2 viral isolates (central) ¹²		X ⁶		X		X	X	X		X	X		(X) ¹³	

Study Day (Visit windows) ⁴	Screening ¹	Treatment Period											EOT ²	Follow-Up Period ³
	-7 to 1	1	2	3	5	7	10	14 (±1)	17 (±1)	21 (±1)	28 (±3)	56 (±5)	90 (±5)	Biweekly up to 180 (±5)
Telephone Follow-Up Visit														X
Patient diary ¹⁴	X	X											(X)	
SARS-CoV-2 infection related signs and symptoms assessment ¹⁵	X	X ⁶	X	X	X	X	X	X	X	X	X	X	X	X
NEWS2	X	X ⁶	X	X	X	X	X	X	X	X	X	X	X	
Immunogenicity sampling (central)		X ⁶				X		X			X	X	X	
Viral serology for SARS-CoV-2 antibody ¹⁶		X ⁶				X		X			X	X	X	
Physical Examination	X	X ⁶											X	

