 16. Viral serology for SARS-CoV-2 antibody test with assays detecting serum antibodies against SARS-CoV-2 will be performed locally using the serum samples (if the assay is available).
 17. To determine eligibility, clinical laboratory testing will be performed at the local laboratory at Screening. Clinical laboratory testing (clinical chemistry, hematology, and urinalysis) for all visits including Screening will be analyzed at the central laboratory.

Clinical chemistry	Total protein, serum bilirubin (total, direct), ALT, AST, alkaline phosphatase, γ -glutamyl transferase, blood urea nitrogen, creatinine, creatine kinase, creatine kinase-myocardial band isoenzyme, troponin (I or T, only one applicable), albumin, sodium, potassium, calcium, chloride, inorganic phosphorus, glucose, lactate dehydrogenase, total cholesterol, triglyceride, high-density lipoprotein cholesterol, and CRP
Hematology	Red blood cells, ESR (local), total white blood cell count, absolute neutrophil count, eosinophil count, lymphocyte count, platelet count, hemoglobin, mean corpuscular volume, mean corpuscular hemoglobin, mean corpuscular hemoglobin concentration, and hematocrit
Urinalysis	Bilirubin, blood, glucose, ketones, leukocytes, nitrite, pH, protein, specific gravity, urobilinogen, and microscopic examination of white blood cell count, red blood cell count, and bacteria.

18. Blood pressure, heart and respiratory rates, SpO₂ and body temperature will be measured after the patient has rested quietly for at least 5 minutes. SpO₂ will be measured while breathing normal room air. Temperature will be measured using tympanic thermometer throughout the study.
19. All scheduled 12-lead ECGs must be performed locally after the patient has rested quietly for at least 5 minutes. Regardless of the 12-lead ECG result, further cardiological evaluation can be performed at the investigator's discretion. If the patient has a 12-lead ECG result performed within 7 days prior to the study drug administration even before signing the ICF, the result can be used for the Screening assessment.

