11.1.3. Viral Serology for SARS-CoV-2 Antibody

Viral serology for SARS-CoV-2 antibody test with assays detecting serum antibodies against SARS-CoV-2 will be performed locally using the serum samples (if the assay is available). Viral serology for SARS-CoV-2 antibody result will be summarized on the ITTI Set by each treatment group at each scheduled visit using frequency table.

12. Changes in the Planned Analysis

- For patients who had negative result at Day 1 or missing Day 1 result of RT-qPCR, the ITTI Set will also include these patients if they are confirmed SARS-CoV-2 infection positive by Day 2 or Day 3. These patients can also be considered as infected since the virus was detected at Day 2 or Day 3.
- All expression or text regarding phenotype will be deleted in SAP since phenotype was not analyzed.

13. Reference List

International Council for Harmonisation (ICH) Assembly. ICH E9: Statistical principles for clinical trials – Step 5. 01 September 1998.

US Department of Health and Human Services. (2010). National Institutes of Health, National Cancer Institute. Common Terminology Criteria for Adverse Events (CTCAE) Version 5.0. Available from: <http://evs.nci.nih.gov/ftp1/CTCAE/About.html>.

Chan, I. S. F., and Zhang, Z. (1999). Test-Based Exact Confidence Intervals for the Difference of Two Binomial Proportions. Biometrics 55:1202–1209.

Schoenfeld, D. (1981). The asymptotic properties of nonparametric tests for comparing survival distributions. Biometrika. 68 (1): 316–319.

CDER, CBER, Multiple Endpoints in Clinical Trials. Guidance for Industry. Draft Guidance. January 2017. Available from: <https://www.fda.gov/files/drugs/published/Multiple-Endpoints-in-Clinical-Trials-Guidance-for-Industry.pdf>

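### Post-dose SARS-CoV-2 serology is run locally and unmasked; where a site's assay detects spike or RBD IgG, it can point to the arm, because CT-P59 is itself such an antibody

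*Protocol*

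**What the plan says.** - **Where and when.** Protocol 6.4 says the SARS-CoV-2 antibody test "will also be performed locally using the serum samples (if the assay is available", and footnote 16 of Table 11-2 repeats this for Part 2: "assays detecting serum antibodies against SARS-CoV-2 will be performed locally using the serum samples (if the assay is available". The table row "Viral serology for SARS-CoV-2 antibody" is marked on Day 1 (pre-dose) and on Days 7, 14, 28, 56 and 90. SAP 11.1.3 and SAP Appendix 1 keep the testing local.
- **What is infused.** Protocol 1.2: "CT-P59 is a human monoclonal antibody targeted against SARS-CoV-2 spike protein". Protocol 5.2.1 describes the vial as a "solution of SARS-CoV-2 RBD binding monoclonal antibody".
- **Who must stay blind.** Protocol 5.4: "This study will be double-blind, and will remain blinded to the investigator". It extends this to designated site staff and patients until the final study report. Drug preparers and the predefined sponsor and CRO teams are the exceptions.
- **How the results are used.** SAP 11.1.3: "Viral serology for SARS-CoV-2 antibody result will be summarized on the ITTI Set by each treatment group at each scheduled visit".
- **What is absent.** Neither document names the assay antigen. Protocol 5.4 and 5.4.1 and SAP 5.3 contain no rule that withholds post-dose serology from anyone. By contrast, the PK assay (Protocol 6.3), the anti-drug antibody assays (6.2.4) and viral shedding (Table 11-2) are all assigned to a central laboratory.

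**The concern.** A serology kit that detects IgG against spike or RBD cannot distinguish a patient's own antibody from infused CT-P59. Local testing with no masking rule would then put a result that carries information about the arm in the hands of staff who must remain blinded. This starts at Day 7, inside the Day 28 window of the primary endpoint.

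Several outcomes depend on site judgement after that point:

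- admission and in-hospital treatment, which feed the hospitalization component in SAP 9.1;
- rescue therapy, a secondary endpoint that, like hospitalization, also censors time to clinical recovery (SAP 9.2);
- causality, which under Protocol 6.2.1.3 decides whether worsening COVID-19 is reported as an adverse event at all;
- suspected antibody-dependent enhancement (ADE), which is the investigator's call (Protocol 6.2.15).

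There is a second, separate problem. On a spike/RBD assay, the SAP 11.1.3 table by arm and visit would largely show circulating drug in the CT-P59 column, not immune response.

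**Working it through.** **Inputs.** From Protocol Table 1-1 (simulated, 40 mg/kg): AUC0-72h = 40,364 and AUC0-168h = 68,952 µg·hr/mL. From Protocol 1.3.2: serum level 99.5 µg/mL at 28 days and a lung factor of 0.15. From Protocol 7.5: 650 per arm, of whom 411 are high-risk. The plan gives no figure for serology or unblinding. The one related figure it derives does reproduce: 99.5 × 0.15 = 14.9 µg/mL in lung.

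**Step 1: is drug present at the serology visits?**

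- Mean level over 0–168 h = 68,952 / 168 = 410 µg/mL.
- Mean level over 72–168 h = (68,952 − 40,364) / 96 = 298 µg/mL.
- Around Day 28: 99.5 µg/mL.

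Drug is therefore circulating in quantity at Days 7, 14 and 28.

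**Step 2: what does one result tell the site?** Assume that the local assay detects spike/RBD IgG and reads positive in every CT-P59 patient. Let s be the share of placebo patients who are seropositive at that visit from their own infection. The documents do not give s, so a range is shown. With 1:1 allocation:

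- P(CT-P59 | positive) = 0.5 / (0.5 + 0.5s) = 1 / (1 + s).
- P(placebo | negative) = 1 under these assumptions.
- Share of arms guessed correctly = 0.5 + 0.5(1 − s) = 1 − s/2.
- Placebo patients identified by a negative result = 650(1 − s), or 411(1 − s) among high-risk patients.

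| s | P(CT-P59 given positive) | Arms guessed correctly | Placebo identified, of 650 | High-risk placebo identified, of 411 |
|---|---|---|---|---|
| 20% | 83% | 90% | 520 | 329 |
| 50% | 67% | 75% | 325 | 206 |
| 80% | 56% | 60% | 130 | 82 |
| 95% | 51% | 52.5% | 33 | 21 |

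**Step 3: scale by assay.** The counts assume that every patient is tested with a spike/RBD assay. If only a fraction f are, they become 650(1 − s)f and 411(1 − s)f. With nucleocapsid-only assays, or no local assay, f = 0 and there is no direct drug signal. The documents do not allow f to be narrowed.

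**Step 4: which events are exposed?** Day 7 is the first post-dose test, so events before that result are untouched. Events between it and Day 28 are potentially exposed.

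**The case against.** **Much of the counter-case stands.**

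- The antigen is unstated and testing is done only where an assay is available, so exposure may vary by site from none to substantial.
- All patients are enrolled as infected, up to 7 days after symptom onset, and SAP 7.1 allows for seropositive patients on Day 1. Placebo patients will seroconvert too, so a positive result is only suggestive and becomes less so at later visits.
- That the investigator sees the result is inferred from local testing. A laboratory manual outside these documents might mask it.
- SAP 9.1 narrows discretion. Admission alone is not an event: it takes at least 24 hours of acute care plus a qualifying treatment. An oxygen event needs at least 24 hours and room-air SpO2 of 94% or lower. Use of remdesivir or tocilizumab during admission remains a site decision.

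**Stronger readings that a reader might infer, and why they fail.**

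- *Every treated patient visibly turns IgG positive and IgM negative.* SAP 7.1 mentions IgG and IgM only for Day 1 serostatus. The phrase "Human immunoglobulin G1" appears only in the abbreviation list, and no sentence assigns that isotype to CT-P59. The argument needs only the stated spike/RBD target.
- *A Day 28 level about 4,000 times the EC90 (99,500 / 25.09 = 3,966) proves that assays read positive.* The EC90 is an in vitro neutralization value, not a serology cut-off.
- *Protocol 5.4 leaves investigators outside the blind.* It names them as blinded. What is missing is an operating rule for this test.
- *A few influenced decisions would overturn the trial.* The design implies about 29 versus 12 events (411 × 7.1% and 411 × 2.9%). Removing six placebo events moves an unstratified chi-square p-value from 0.0065 to 0.057. Nothing ties those six events to unblinding, and the primary test is a stratified CMH test, so this is not an estimate of bias.
- *The pre-unblinding medical reviews are compromised.* That depends on whether the reviewers can see post-dose serology, which the documents do not say. The high-risk list rests on baseline facts in any case.

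**Conclusion.** The point holds in conditional form, with medium confidence. The plan directs sites that must stay blinded to run, after dosing, a test whose antigen is unspecified and whose results are not masked, while large amounts of an anti-spike/RBD antibody circulate in one arm.

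Where the assay detects spike or RBD IgG, a negative result strongly suggests placebo and a positive one weakly to moderately suggests CT-P59. At f = 1 and s from 20% to 80%, correct guessing of the arm runs from 90% down to 60%. With nucleocapsid assays there is no direct signal. These figures rest on assumed values of s and f and on every treated patient reading positive. They measure information about the arm, not bias in the endpoint, and the documents do not support any estimate of that bias.

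On spike/RBD assays, the post-dose comparison of arms in SAP 11.1.3 is not interpretable as immune response. That table is exploratory, and the pre-dose Day 1 serostatus is unaffected. This is a cheap improvement. It does not show that the primary analysis is invalid.

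**What to change.** **Conduct (Protocol 6.4, Table 11-2 footnote 16, laboratory manual).** Keep the Day 1 pre-dose test local. Do not run or release post-dose serology at sites. Test it centrally, for example on the immunogenicity serum already drawn at the same visits, and withhold results from the blinded sponsor team until the Day 28 unblinding and from sites for as long as Protocol 5.4 keeps them blinded. Alternatively, require an assay that does not detect the drug.

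**Analysis (SAP 11.1.3).** Record the assay target for each result. Compare arms after dosing only on assays that do not detect spike/RBD antibody, and list the rest.

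**Data already collected.** The SAP cites a blinded data review meeting that had already taken place, so the conduct change may come too late for some patients. For them, add a descriptive table of the primary result by site assay type: spike/RBD, nucleocapsid, not tested. Assay type is not randomized and the planned event count is small, so this is context and not a test. Do not count only events before the first post-dose result. That would cut a Day 28 endpoint at roughly Day 7, at a time that depends on attendance and on local assay availability, and would discard genuine later events.

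**Cost.** A footnote and laboratory-manual change, a short SAP addition, one descriptive table and a small central-testing workload. No extra visit or blood draw is scheduled. Sites lose real-time post-dose serology, but no decision in the protocol uses it. Sample size and alpha are unchanged.

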11.4 New York Heart Association Functional Classification

As defined in [Zhang et al, 2018](#), the New York Heart Association (NYHA) classification is used in patients with heart failure.

Class	Symptoms
I (Mild)	No limitation of physical activity. Ordinary physical activity does not cause undue fatigue, palpitation, dyspnea (shortness of breath).
II (Mild)	Slight limitation of physical activity. Comfortable at rest. Ordinary physical activity results in fatigue, palpitation, dyspnea (shortness of breath).
III (Moderate)	Marked limitation of physical activity. Comfortable at rest. Less than ordinary activity causes fatigue, palpitation, dyspnea.
IV (Severe)	Unable to carry on any physical activity without discomfort. Symptoms of heart failure at rest. If any physical activity is undertaken, discomfort increases.

11.5 National Early Warning Score 2 (NEWS2)

Physiological parameter	Score						
	3	2	1	0	1	2	3
Respiratory rate (breaths per minute)	≤8		9-11	12-20		21-24	≥25
SpO ₂ Scale 1 (%)	≤91	92-93	94-95	≥96			
SpO ₂ Scale 2 (%)*	≤83	84-85	86-87	88-92 ≥93 on room air	93-94 on oxygen	95-96 on oxygen	≥97 on oxygen
Room air or oxygen?		Oxygen		Room air			
Systolic blood pressure (mmHg)	≤90	91-100	101-110	111-219			≥220
Heart rate (beats per minute)	≤40		41-50	51-90	91-110	111-130	≥131
Consciousness				Alert			CVPU
Body temperature (°C)	≤35.0		35.1-36.0	36.1-38.0	38.1-39.0	≥39.1	

Abbreviations: C = confusion; P = pain; U = unresponsive; SpO₂ = Saturation peripheral oxygen; V= voice.

* For patients with hypercapnic respiratory failure (blood gas analysis may be locally done by the investigator's discretion) and requiring supplemental oxygen, a prescribed oxygen saturation target range of 88 to 92% is recommended, and SpO₂ Scale 2 will be used to score the oxygen saturation of the NEWS2. The decision to use SpO₂ Scale 2 should be made by the investigator. In all other circumstances, SpO₂ Scale 1 will be used for scoring NEWS2.
